a. We hypothesize that participants randomized to ActiveGOALSV2 + PAT will have significantly larger (a) changes in step counts/day and % meeting moderate-vigorous physical activity goal of 150 minutes/week (to 12 months) compared to the active PAT control group. Primary outcomes will include changes in step/day and meeting the activity goal from validated research-grade PATs. Secondary outcomes will include changes in body weight, blood pressure, glycemic control, and cholesterol from study collected clinical outcomes and health questionnaires.

b. EHR data will also be used to assess program success, including program reach (comparing patients enrolling/not enrolling) and examining relationships between changes in EHR-recorded cardiometabolic outcomes and primary PA outcomes from PATs. Finally, pre-enrollment factors will be examined in relation to program success, toward better future identification of patients who may benefit from referral to programs for PA improvement. Results of this aim will be used toward developing a technology enabled referral system to an appropriate lifestyle intervention strategy with program evaluation methods that use EHR data

2. * Describe the relevant prior experience and gaps in current knowledge including preliminary data. Provide for the scientific or scholarly background for, rationale for, and significance of the research based on existing literature and how it will add to existing knowledge:

Advice from clinicians can significantly influence lifestyle behaviors. Following the American College of Sports Medicine, the American Heart Association (AHA) has recently issued a statement endorsing clinical physical activity prescription

programs. [15,18,38] In their statement the AHA outlines advantages of clinical PA advice and referral, including improved patient outcomes and lower healthcare costs.[38] Clinically administered advice on physical activity has also been shown to increase patient satisfaction with clinical care.[6,7] However, the concept of treating low physical activity levels through clinical practice is relatively new and often not part of standard care.[8-11]

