This proposal will build on existing efforts to advance physical activity referral within routine clinical care. The inclusion of important stakeholders,[23-26] effective use of existing clinical resources,[27,28] and better integration of technology, including electronic health record (EHR) systems and body worn/ remote monitoring,[25,27-31] may increase the success of clinical physical activity referral programs, respectively. Clinical referral to physical activity is a multifaceted issue in which input from a number of different stakeholder groups is likely needed to ensure program success. [38-40] Evidence from surveys of health professionals suggest that existing clinical programs for physical activity advice and referral do not adequately consider the needs of clinical teams;[23-26,41] physical activity prescription programs usually put the burden on the clinician to prescribe and follow-up on patients and on patients to determine how they will reach the prescribed goal. [18,40] While referral to outside community-based programs are typically programs for weight-loss and physical activity (DPP-based), that may provide status updates on weight, but not on physical activity changes.[42] In relation to this, while self-monitoring of lifestyle behaviors has been shown to be an effective tool in behavior change, participants also find it to be difficult and it is not often maintained.[43-46] Most people currently own a PAT-enabled device and 20% of the population may be tracking their physical activity at any given time.[47] With increased interest in PATs, fully integrating them into intervention may help relieve tracking burden on participants and increase program participation and recruitment.[45] Additionally, integration of data from PATs into clinical EHR systems has been identified as a valuable way of communicating patient physical activity levels, but there is currently no standardized system for doing so.[38,48] We will further existing work by fully integrating PATs into an online lifestyle intervention and by outlining specific procedures for integrating PATs into a local Epic-based EHR. The design process will include important stakeholders, with metrics of stakeholder engagement collected.

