table. Participants will be asked to rest quietly with feet flat on the floor for five minutes. The cuffed arm will be raised for 5 seconds after each inflation and a wait of 30 seconds will occur between each blood pressure reading. Blood pressure will be repeated twice with the average computed. If it is not possible to measure blood pressure in the right arm, the left arm should be utilized and noted in the patient record.

HbA1c: HbA1c will be assessed using a point of service hba1c monitor. Participants will be seated for the finger stick. Hand warmers may be used prior to the finger stick to ensure good blood flow. A sterile lancet will be used to prick the 3rd or 4th finger tip of the non-dominant hand- after the site has been prepped with a 70% isopropyl alcohol swab and is thoroughly dry. The first drop of blood will not be used, if needed the finger will be gently squeezed to obtain a second drop of free-flowing blood. A fresh finger stick will be applied and inserted into the monitor. Results will be available within 5-10 minutes.

Intervention Delivery: ActiveGOALS uses online self-directed once a week sessions with brief remote personalized e-coaching support. Social-cognitive behavior change theory and related strategies, including barrier recognition and problem-solving are included. There are 13 (20-25 minute) structured educational lessons with interactive workbook pages delivered via the GOALS online platform. After the 13 week “core intervention”, participants will continue to have access to resources on ActiveGOALSV2 for 9 more months and will receive once a month contact including a semi-personalized email from their coach and a link to online materials on a specific behavior maintenance topic (10 minutes in length). Printable workbook pages, resources, and tracking tools will also be available. The topics for the maintenance materials will be determined from output of satisfaction/ experience questionnaires administered to current ActiveGOALSV1 participants (PCOR K12 funded project) and already developed proven maintenance materials from DPP and DPP GOALS.

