with feet together. Waist is measured using a cloth tape around the abdomen, with midpoints marked horizontally between highest point of the iliac crest and lowest part of the costal margin in the mid-axillary line. Both sides of the waist should be marked. The subject will be asked to have arms at side and to breathe in, out and hold, and then the measurement is taken. Waist measurement is recorded to the nearest quarter inch. The measure will be repeated twice. If waist measures differ by more than one-half inch, a third measurement will be recorded.

In-person clinic visits will be conducted at an on-campus clinic by trained clinic personnel, who will be blinded to randomization arm (to ensure rigor). Participants will be given instructions for the fasting blood draw (8-12 hours). Previously validated questionnaires will be administered (via computer) related to medical history/ medications, demographics/ education, healthy lifestyle habits, self-efficacy/confidence, quality of life (using PROMIS 29 and EQVAX from EQ5D), cost, patient experience; all previously used in the current K12 funded ActiveGOALSV1 study. Additional output from ActiGraph monitors (average minutes/day spent in MV physical activity, light, and sedentary) may be examined, as will data collected from PAT devices and the ActiveGOALSV2 platform. Blood samples (glucose, insulin, LDL and HDL cholesterol, triglycerides) will be drawn and processed at a Quest™ labs. Participants will be encouraged to fast for their appointment and get go to the Quest™ labs near UPITT, but can go to a Quest™ location convenient to them (25+ locations around Pittsburgh), within 10 days after the visit. To control for dietary change, participants will be asked if they attempted weight-loss through dietary change during intervention, questions on sugary beverage, water, vegetable, and protein intake will also be asked

The time commitment for accessing this version of the GOALS program will vary, but will generally not exceed 1 hour each week.

Accessing GOALS. Most participants will choose to access the GOALS website from home; others may do so from work, at a friend or family member's home, and/or from a public location, such as a library. The GOALS platform is PC- and Mac-compatible only; it does not run on any mobile devices.

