Coverpage

Title: Advancement of Clinical Referral to Physical Activity for Cardiometabolic Disease Prevention

Brief Title: The Clinical Referral to Activity Study

NCT: NCT04743856

Date Created/Modified: November 3, 2025

Statistical Analyses

6.1.6 Statistical Analyses: For our primary outcomes, we hypothesize that participants randomized to ActiveGOALSV2 + PAT will have significantly larger (a) increases in step counts/day and % meeting MVPA goal of 150 minutes/week (to 12 months) compared to the active PAT control group. Descriptive analyses and graphic displays will be used to identify outliers, missing data, and pattern of attrition. To ensure rigor, the primary analytic strategy will be a linear or generalized mixed-effect models approach in which treatment group, time, and time by group interaction are treated as fixed effects, and subject is treated as a random effect to account for individual subject variability (two sided hypothesis test; .05 level). Mixed models are applicable to longitudinal datasets that contain missing observations, (assuming data is missing at random). Regression modeling will be conducted to adjust for important covariates. We will perform similar analyses to examine changes in secondary outcomes. Descriptive statistics on patient experience, beliefs/attitudes related to maintenance of PA changes, and program cost will also be reported. Mixed models are used to help account for missing data and no adjustments will be made for multiple comparisons.

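### A diet item measured after randomisation is collected for statistical control, and the open covariate plan leaves room for it in the between-arm models for secondary outcomes

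*Protocol*

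**What the plan says.** Protocol, Research Activities, item 1, at the end of the secondary-outcome description: "To control for dietary change, participants will be asked if they attempted weight-loss through dietary change during intervention". The same sentence goes on: "questions on sugary beverage, water, vegetable, and protein intake will also be asked". Neither the protocol nor the SAP says anything further about how these answers will be analysed.

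SAP 6.1.6, and the matching text in the protocol's power-analysis item (Study Design, item 8), describe the primary strategy as a mixed model in which "treatment group, time, and time by group interaction are treated as fixed effects, and subject is treated as a random effect". Two further statements follow: "Regression modeling will be conducted to adjust for important covariates" and "We will perform similar analyses to examine changes in secondary outcomes". No covariate is named, and none is required to be measured before randomisation.

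Protocol, Study Aims, item 1, lists the outcomes concerned: "Secondary outcomes will include changes in body weight, blood pressure, glycemic control, and cholesterol from study collected clinical outcomes". Study Design, item 3, adds waist circumference. Research Activities, item 1, warns that the secondary analyses may be underpowered, but says their findings will inform the design of a larger trial of cardiometabolic outcomes.

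**The concern.** Dieting to lose weight during the intervention happens after assignment and may be changed by it. Only the intervention arm receives the lessons, weekly coach feedback and monthly maintenance contacts. Conditioning on such a variable has two effects. It takes out whatever part of the programme's effect runs through diet. And if something unmeasured, such as motivation, drives both dieting and weight, it brings back confounding that randomisation had removed.

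At stake are the between-arm estimates for weight, waist, blood pressure, glycaemia and lipids, which are the estimates meant to be carried into the follow-on trial. A diet-adjusted figure read there as the effect of assignment could mislead its planning.

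**Working it through.** The plan gives no figure for diet or for its effect on any outcome, so there is nothing to reproduce. The check is a reading of the text followed by an illustration on assumed inputs.

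**Text.**
1. Timing: the item asks about behaviour during the intervention, so it is post-randomisation.
2. Purpose: the protocol gives it as control, not description.
3. Route into a model: the main mixed model has only group, time, their interaction and a subject effect. The one place where a further variable could enter is the covariate-adjustment sentence, which is open and extends to the secondary outcomes.
4. Route from arm to diet: maintenance topics for the intervention arm draw partly on "already developed proven maintenance materials from DPP and DPP GOALS". The background section (Study Aims, item 2) describes outside community programmes as "typically programs for weight-loss and physical activity (DPP-based". This makes an effect of the arm on dieting possible. It does not establish one.

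**Illustration (all inputs assumed).** Direct effect on weight -1.0 kg; dieting lowers weight by 2 kg; 30% of controls diet.

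Total effect = direct effect + (difference in dieting rate) × (diet effect).

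- 30% versus 30%: -1.0 + 0.00 × (-2) = -1.0
- 30% versus 40%: -1.0 + 0.10 × (-2) = -1.2
- 30% versus 50%: -1.0 + 0.20 × (-2) = -1.4
- 30% versus 60%: -1.0 + 0.30 × (-2) = -1.6

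With no common cause of dieting and weight, the diet-adjusted model recovers only the direct effect, -1.0. The common-cause column is from a simulation of one million participants. It has an unmeasured standard normal factor that lowers weight by 1 kg per SD and correlates 0.5 with the latent tendency to diet, and residual SD 3 kg.

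| Dieting, control vs intervention | Total effect (kg) | Adjusted, no common cause | Adjusted, common cause |
|---|---|---|---|
| 30% vs 30% | -1.0 | -1.0 (no bias) | about -1.0 (no bias) |
| 30% vs 40% | -1.2 | -1.0 (17% short) | -0.924 (23% short) |
| 30% vs 50% | -1.4 | -1.0 (29% short) | -0.847 (about 40% short) |
| 30% vs 60% | -1.6 | -1.0 (38% short) | -0.756 (53% short) |

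The departure therefore runs from zero to about half the total effect, depending mainly on how far the arm changes dieting. A common cause that raised both dieting and weight would push the adjusted estimate the other way.

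**Scale in this trial.** 54 enrolled with 20% attrition leaves 54 × 0.8 = 43.2, or 21.6 per arm if allocation is 1:1 (the ratio is not stated). With an assumed SD of weight change of 4 to 6 kg, the standard error of the arm difference is SD × √(2/21.6) = 0.304 × SD, or 1.22 to 1.83 kg. A shift of 0.4 kg is 0.4/1.83 = 0.22 to 0.4/1.22 = 0.33 standard errors.

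**Scale for the follow-on trial.** At a fixed SD, required sample size varies with 1/effect². Planning on -1.0 instead of -1.4 multiplies it by (1.4/1.0)² = 1.96.

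**The case against.** A reader might infer that the secondary analyses will condition on diet and will be biased. The documents do not support that. No passage puts diet into a between-arm model, the SAP never mentions it, and the protocol's stated purpose could be met by a supplementary or sensitivity analysis. This stands, so the point is about what the plan permits and signals, not about a specified model.

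A second objection is that the programme targets physical activity. Its goals and tracking tools cover steps and activity minutes, and no dietary lesson is described. That also stands: an effect of the arm on dieting is plausible but not shown, and without one there is no bias.

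Third, the intake questions may also be asked at baseline, since Research Activities, item 1, schedules all outcome measures at baseline, 6 and 12 months. Baseline intake would be a legitimate covariate. The objection reaches only answers about the period after randomisation.

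Fourth, on the assumed figures the shift is small beside the sampling error in a trial of 54, and the secondary analyses are already described as possibly underpowered. This limits the consequence within the trial. It does not remove the point, because the estimates are meant to be carried forward, and a systematic shortfall would not average out the way sampling error does.

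What remains is that control is the only analytic purpose the documents give this item, the adjustment step is open to it, and nothing marks a diet-adjusted result as anything other than a treatment-effect estimate.

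**Conclusion.** The concern holds in a conditional form. The protocol states an intent to control for a post-randomisation variable, and the covariate plan would allow this in the secondary between-arm models. If that is done, and if assignment influences dieting, the result does not estimate the total effect of assignment.

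The size cannot be derived from the documents. It starts at zero. The example of -1.4 kg estimated as -1.0 kg rests wholly on assumed dieting rates and effects, and should not be quoted as an expected bias.

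A reader might also take this as a threat to the primary results. The documents do not support that reading: the main mixed model for steps and the activity goal, as written, contains no diet term, and the sample size of 54 is unaffected. The point is a modest one about secondary estimates, worth correcting because the correction is nearly free.

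**What to change.** 1. In SAP 6.1.6 and the matching protocol text, list the adjustment covariates and state that covariate-adjusted between-arm effects use only variables measured before randomisation. Baseline dietary intake may be included if it is collected. If the baseline outcome is already part of the mixed model's response, do not also add it as a covariate.
2. Report diet attempts and change in intake by arm, descriptively.
3. Label any model that adjusts for diet during the intervention as exploratory or as a mediation analysis, and do not present its group coefficient as the effect of assignment.
4. Reword the protocol sentence to match, for example: *Diet change during the intervention will be described by arm; any analysis adjusting for it is exploratory.*

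The cost is wording in two documents, with no change to data collection or sample size. The one thing given up is that a diet-adjusted result becomes exploratory.

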*** Provide a justification and describe the qualifications of the individuals who will obtain consent:**

This is a minimal risk study. For the phone screening, in-person screening, and main consent, the consenting process will either be conducted by the PI or a trained staff person who has completed all CITI modules for human subjects research and has been trained in the consenting process.

For the main study consent: Eligible participants will be sent a consent form to read. Interested participants will be scheduled for an on-campus clinic visit where they can ask questions and be consented for the study. Baseline measures will be collected at the visit.

Consent Forms

1. Consent Forms:

Document	Category	Date Modified	Document History
View Inperson Screen Consent(5)	Consent Form	2/23/2022	History
View Main Study Consent(6)	Consent Form	2/23/2022	History

Refer to the following templates and instructional documents:

- Guidance - [Consent Wording](#)
- Template - [Consent Document - Short Form](#)
- [HRP-090 - SOP - Informed Consent Process for Research](#)
- [HRP-091 - SOP - Written Documentation of Consent](#)

Waiver to Document Informed Consent

This waiver to document informed consent can be requested for any or all participants, for any or all procedures (e.g., a verbal or computerized consent script will be used, but the subjects will not be required to sign a written informed consent document, such as with phone screening).

1. * Identify the specific research procedures and/or the specific subject populations for which you are requesting a waiver of the requirement to obtain a signed consent form:

Phone Screening

2. * Select the regulatory criteria applicable to your request:

45 CFR 46.117(c)(1) That the only record linking the subject and the research would be the consent document and the principal risk would be potential harm

resulting from a breach of confidentiality. Each subject will be asked whether the subject wants documentation linking the subject with the research, and the subject's wishes will govern.

45 CFR 46.117(c)(2) That the research presents no more than minimal risk of harm to subjects and involves no procedures for which written consent is normally required outside of the research context

45 CFR 46.117(c)(3) If the subjects or legally authorized representatives are

members of a distinct cultural group or community in which signing forms is not the norm.

*** Address why the specific research procedures for which you are requesting a waiver of the requirement to obtain a signed consent form presents no more than minimal risk of harm to the research subjects:**

Initial screening: Interested persons will be contacted by phone. The attached script will be used to complete the telephone screening.

*** Justify why the research involves no procedures for which written informed consent is normally required outside of the research context:**

We believe that the phone screening involves no more than standard questions that might be asked in scheduling a routine visit for individuals with cardiometabolic risk factors and therefore presents no more than minimal risk of harm to subjects."

3. * Upload Scripts:

Document	Category	Date Modified	Document History
View script to schedule in person screen(0.01)	Waiver Script	2/23/2022	History
View Screening Phone Script_2_22_22.docx(3)	Waiver Script	2/23/2022	History
View Telephone Screening Guide.docx(0.01)	Waiver Script	4/28/2020	History

Medical Records

1. You are required to submit this study to the Research Informatics Office, Health Record Research Request (R3). Per UPMC Policy HS-RS0005, all research projects that access or involve UPMC electronic protected health information (e- PHI) must be submitted to R3, with the exception of clinical trials that are contracted through the UPMC Office of Sponsored Programs and Research Support (OSPARS).

Complete the R3 intake form available at <http://rio.pitt.edu/services>. An R3 representative will conduct a review. You will be notified once your R3 review is complete or if anything further is needed.

*** Describe the protected health information that will be collected from the covered entity and/or the research derived information that will be placed into the medical records:**

Body mass index, blood pressure, and blood glucose and the diagnosis of the following conditions: diabetes, coronary artery disease, stroke, arrhythmia, congenital heart defect, cardiomyopathy, abdominal aortic aneurism, and myocardial infarction will be collected. Reports to physicians will include participant changes in physical activity and session attendance.

2. *** Describe what protected health information will be obtained from a non-UPMC/Pitt covered entity for research purposes and how the HIPAA requirements will be met:**

Only if necessary, to confirm inclusion/exclusion criteria:

Height and weight taken within the last 18 months

Diagnosis of coronary artery disease, stroke, arrhythmia, congenital heart defect, cardiomyopathy, abdominal aortic aneurism, or previous myocardial infarction.

Diagnosis/ current treatment of high blood pressure, pre-diabetes

Recorded blood pressure, Hba1c, blood glucose, cholesterol, triglycerides within the past 18 months.

Information will be requested from the otherwise eligible participant. Individuals who have been screened as eligible from the phone interview, but are not UPMC patients, will be asked to either have their physician sign a statement verifying that they meet the eligibility criteria and identifying which of the three cardiometabolic criteria pertains to them (overweight/obese, high blood pressure, high glucose) or the participant can bring a copy of their medical records showing proper diagnosis/ current treatment of any above listed conditions to an in-person screening that will take place prior to their consent/in-person baseline visit. The reviewing staff member will record the presence/absence of diagnosis/treatment on a de-identified study clinic form, which will be signed by the staff member and verified by another staff member and the study PI. The medical record will be returned to the participant and the de-identified study form will be stored in a secure location with the participant files (in the department of Epidemiology). Use of medical records will also be reported to [name], who will review the criteria used to determine eligibility/ ineligibility.

Electronic Data Management

1. * Will only anonymous data be collected (select **NO** if identifiers will be recorded at anytime during the conduct of the study)?

Yes No

Select all identifiers to be collected during any phase of the research including screening:

Name:		Internet Protocol (IP) Address:	
E-mail address:		Web Universal Resource Locators (URLs):	
Social security #:		Social security # (for Vincent payment only):	
Phone/Fax #:		Full face photo images or comparable images:	
Account #:		Health plan beneficiary #:	
Medical record #:		Device identifiers/serial numbers:	
Certificate/license #:		Vehicle identifiers/serial #/license plate #:	
		Biometric identifiers, finger and voice prints:	

a: Will you be collecting any of the following **location data**: geographic subdivisions smaller than a State such as street address, city, county, precinct, zip, geocodes, etc.? Yes No

* b: Will you be collecting any **date information** such as birth date, death, admission, discharge, date of surgery/service? Yes No

c: List any other unique identifying numbers, characteristics or codes related to an individual that are to be collected:

d: Will you be collecting any data subject to the General Data Protection Regulation (GDPR)? Yes No

Social security numbers may be used to obtain medical record data for a participant.

* e: Provide a justification for recording Social Security numbers including why it's required, where it's stored, how it's protected and who will have access:

Data is also collected for Vincent payment. Social security numbers are obtained at the in-person baseline visit and are typed directly into Vincent. They are not written or stored anywhere else.

For ALL identifiable data collected, will you be coding the data by removing the identifiers and assigning a unique study ID/code to protect the identity of the participant? Yes No

* the identifiers and assigning a unique study ID/code to protect the identity of the participant?

* Will the data be HIPAA de-identified?

Yes No

Backup and security policies will help ensure the safety and confidentiality of electronic data. Backup procedures include system backup, daily incremental backup and off-site fireproof storage. Security procedures include logon and link password protection, remote password logon and dial-back modems, and for internet access, separate web servers which use SSL and encryption algorithms. Regularly updated virus scanning software is used routinely to check personal computers for computer viruses. University computing facilities provide support in the event of a disaster. The University maintains confidentiality of patient data and emerging results per a confidentiality policy, which every staff member is required to sign annually.

Briefly describe your plan to store
* coded data separately from the
identifiable data:

De-identified data will be stored on a passcoded database on PITT servers. Paper records will be kept in a locked cabinet in a secured room in the graduate school of public health. Identified data will be stored in a separate id passcoded database on Pitt servers and paper records with identified data will be stored in separate files in a locked cabinet within the graduate school of public health

2. During this study, will restricted data as defined by the University's Data Risk Classification matrix (<https://www.technology.pitt.edu/security/data-risk-classification-and-compliance>) be processed, stored, or transmitted?

Yes No

3. * During this study, will sensitive data (<https://www.hrpo.pitt.edu/electronic-data-security>) be collected where disclosure of identifying information could have adverse consequences for subjects or damage their financial standing, employability, insurability, educational advancement, reputation or place them at risk for criminal or civil liability?

Yes No

4. * Select all locations where data will be stored or archived(including e.g., personal / employer laptop or desktop): If you have access to University owned or controlled resources, facilities, or repositories, such as computer servers, please choose that option to comply with the [Research Data Management Interim Policy R1 14](#).

Please note that to address Research Security Requirements, University data must be stored in University owned, controlled, or approved repositories, such as Pitt OneDrive. If UPMC or external electronic repositories must be used, they must be approved by Pitt IT.

Storage Device	Description	Identifiable Data	Sensitive Data	De-Identified/Anonymous Data
View Server: Pitt Department Managed Server	Data accessed on a PITT owned desktop computer may be stored on a server managed by the Epidemiology Department.	yes	no	yes
View PITT owned desktop, laptop or other device	Data will be accessed from a desktop computer in a secured office in the department of Epidemiology at the University of Pittsburgh.	no	no	yes
View Other: Storage device/server	RedCAP managed through PITT CHRC.	yes	no	yes
View Cloud: Pitt Box	Deidentified data may be stored in Pitt Box toward manuscript preparation.	no	yes	yes
View UPMC: Departmental or Hospital Server	Data on ActiveGOALS program usage will be stored on a UPMC server, managed by PITT CHRC. The online program is stored on the server and collects data on usage minute, as well as, workbook page answers completed by participants.	yes	no	no

5. * Select all technologies used to collect data, interact with subjects, or store subject data. Technologies selected in this section may require a Vendor Security Risk Assessment, which can be requested [here](#).

Mobile App

Wearable device (also select mobile app if it will be used with the device)

Text messaging

Web-based site, survey, or other tool

6. * Mobile App – identify all mobile applications, including text messaging apps, used to collect data during any phase of the research:

name	Identifiable
Fitbit	no

7. * Wearable Device - identify all wearable devices used to collect data during any phase of the research:

name	Identifiable
Fitbit wristworn monitor	no
Actigraph GT3x	no

8. * Text Messaging - Identify all uses of SMS / cellular text messaging:

name	Identifiable
Text Message	no

9. * Web Based Technologies – identify all web based technologies to be used to collect data during any phase of the research:

name	Identifiable
View Pitt Redcap Version	
View Other (survey, tool, etc.)	no

Data Safety and Monitoring

1. * Describe your plan to periodically evaluate the data collected regarding both harms and benefits to determine whether subjects remain safe. The plan might include establishing a data monitoring committee and a plan for reporting data monitoring committee findings to the IRB and the sponsor:

A data and safety monitoring plan will be implemented by the Principal Investigator and her primary mentor (Drs. [name] and [name]) to ensure that there are no changes in the risk/benefit ration during the course of the study and that confidentiality of research data is maintained. Each member of the study team will meet with the PI and review confidentiality issues and complete a confidentiality agreement, prior to having contact with research subjects. Investigators and study personnel will meet weekly to discuss the study, including study goals and modifications of those goals, subject recruitment and retention, intervention delivery, progress in data coding and analysis, documentation, identification of adverse events or research subject complaints, and violations of confidentiality) and address any issues or concerns at that time. Minutes will be kept for these meetings and will be maintained in the study regulatory binder. Any instances of adverse events will be reported immediately to the University of Pittsburgh IRB using standard forms and/or procedures that have been established by the IRB.

2. * Describe your plan for sharing data and/or specimens:

Although I do not currently have a data sharing plan, should I decide to share data in the future, I will contact the Office of Research, before sharing de-identified research data/materials to determine whether an agreement needs executed. The research data/documents will be coded and subject identifiers removed prior to access by any external persons.

3. If any research data is collected, stored, or shared in a paper format, address what precautions will be used to maintain the confidentiality of the data:

To maintain the confidentiality of participants' responses, all data gathered, questionnaires, screening information and data forms will be coded with a subject identification number only. A separate file with participants' personal information (e.g., name and phone numbers) will be maintained. All participant information will be stored in a locked file cabinet in the research offices of the University of Pittsburgh. Only the Principal Investigator or a member of this research team will have access to participant files.

Consent forms that identify the participant by name will be sorted in a locked cabinet separately from the remainder of the data collection forms. The data collection forms will be assigned a code number to identify each participant, and participants will be instructed not to identify themselves by name on any of the forms. The data file linking the names and code numbers will be accessible only to the investigators named on this proposal and their research staff. The data collected from each individual will be entered into a computer file by the code number. If the data are used in scholarly presentations or journal articles, the investigators will protect the anonymity of individual participants and will report only aggregate data (e.g., group

means) where appropriate. The Principal Investigator will review data confidentiality processes periodically or as indicated with the project staff.

Return of Results to Subjects or Others

1. * Indicate when personal results will be disclosed:

- Routinely to all research subjects or others
- Only upon the request of a research subject

2. * Indicate how subjects will be informed of their personal results:

Participant results will be mailed via postal mail to the address provided by the participant.

3. * When will the study results be disclosed?

Screening results will be disclosed at the screening visit. Results of clinical assessment measures will be provided within 45 days of receiving all results (from in-person visit and Quest Labs results).

Individual End-of-Study results will be provided after all study measures are completed on all participants.

4. * Describe how results (study results or individual subject results, such as results of investigational diagnostic tests, genetic tests, or incidental findings) will be shared with subjects or others (e.g., subject's primary care provider):

Individual end-of-study subject results will be provided via mail and will be sent to the address provided by the participant. These results will contain a comparison to mean values for the entire study cohort.

End-of-study results will also be sent via postal mail to their referring physician, using the address for the physician provided by the participant. The referring physician will also receive a participant progress report, via postal mail, 4-6 weeks after the participant has started the intervention.

5. * If applicable, is the laboratory performing the analyses on the biological specimens CLIA certified?

Quest Labs in Pittsburgh is CLIA certified. Their licensure current expires 08-07-20. Lic. #39D0938116.

6. * Will the banked biological specimens or data derived from them be provided with subject identifiers to any secondary investigators or external entities?

- Yes
- No

7. * Will research subjects be remunerated in the event of the future commercial development of inventions or products based on the research use of their biological specimens?

- Yes
- No

Risk and Benefits

1. * Enter all reasonably foreseeable risks, discomforts, hazards, or inconveniences to the subjects related to subjects' participation in the research:

View	Research Activity	Clinical Measures- height, weight, waist circumference
	Common Risks	none
	Infrequent Risks	There is a minimal risk that measurement of height, weight, and waist could result in psychological discomfort for the participant. No other risks or events are anticipated.
	Other Risks	No Value Entered
	Research Activity	Clinical measures- blood pressure
View	Common Risks	None
	Infrequent Risks	There is a minimal risk that blood pressure measurement could result in psychological discomfort for the participant. Tightness or rubbing from the measurement device could also cause temporary discomfort. No other risks or events are anticipated.
	Other Risks	No Value Entered
	Research Activity	Phone Screening
	Common Risks	none
View	Infrequent Risks	Questionnaires, Surveys, and Interviews. There is a minimal risk that revealing thoughts and perceptions regarding overall mental and physical functioning could result in psychological discomfort for the participant. No other risks or events related to completing questionnaires or surveys are anticipated. Subjects will be informed that they are free not to answer any questions they do not wish to answer.
	Other Risks	No Value Entered
	Research Activity	Actigraph GT3x+ monitor
	Common Risks	None
	Infrequent Risks	Accelerometer. One potential risk when utilizing the accelerometer although rare, is skin irritation or minimal bruising of the skin from wearing the belt for the accelerometers. It is believed that this should occur in less than 1% of the participants.
View	Other Risks	No Value Entered
	Research Activity	Clinical Measures- Blood Draw
	Common Risks	None
	Infrequent Risks	The risks of taking blood include pain, a bruise at the point where the blood is taken, redness and swelling of the vein and infection, and a rare risk of fainting.

